9.4 STATISTICAL ANALYSES PLAN

Preliminary analyses will include generating descriptive statistics for demographic variables, as well as baseline characteristics and follow-up measures. This includes means and standard deviations for continuous variables, and frequencies and percentages for categorical variables. Ranges will also be examined for outliers and to ensure data integrity. Demographics and baseline characteristics will also be described separately by randomized group. Statistical tests will be performed to compare each of these by randomized group to determine the extent of random imbalance by t-test of chi-square testing, as appropriate. However, the p-values generated by these tests are considered as descriptive rather than as inferential. We would

expect some imbalance between the groups by random chance, owing to the limited sample size. Variables exhibiting imbalance may be considered as covariates in the statistical models described below.

The co-primary outcome of MVPA will be analyzed across the follow-up time points through a general linear mixed model (GLMM). Specifically, the MVPA values at 8 weeks and at 6 months for a given patient will form their response vector for this model. Fixed effects for the primary model will include an indicator for PAS group, an indicator for the 6-month follow-up time point, their interaction (group by time), and baseline MVPA value; a supporting model will also include any covariates that exhibit random imbalance between groups at baseline. Random effects for patients will account for the within-patient correlation induced by the repeated measures design. Formal statistical testing of the group by time interaction term will provide assessment for whether efficacy varies by follow-up time point. A term representing the interaction of PAS-by-baseline value will be included and tested to explore whether participants' starting point might impact how much they improve; it will be removed if non-significant attention. Statistical contrasts will be constructed in order to estimate the effect of PAS versus attention control, separately at 8 weeks and at 6 months; these estimates will inform the sample size estimation of the subsequent trial. Estimated correlations among follow-up time points will also be useful in this regard.

The approach outlined above will be repeated for the co-primary outcome of peak joint loading symmetry during gait, through fitting a separate GLMM. The main difference will be to include walking speed as an additional covariate, as justified in the research strategy. Secondary outcomes will also be analyzed using the same approach, each with its own GLMM.

An exploratory analysis will include KOOS pain scores as a (time-dependent) main effect, as well as their interaction with PAS, to evaluate whether this variable has an impact on intervention effects. This exploratory analysis will be repeated, but using participant-specific changes in KOOS pain scores, to examine how our primary outcomes (MVPA and peak load symmetry during walking) are associated with those changes.

If any of the co-primary or secondary outcomes exhibit distributions that deviate markedly from normality, alternatives will be considered. First, transformations, such as the natural logarithm, will be applied in an attempt to normalize the distribution. If this is not successful in remedying the non-normality, alternatives such as categorizing the variable and applying appropriate categorical data analysis, such as logistic mixed models (with a similar specification as described above for the GLMMs) or logistic models utilizing generalized estimating equations methodology can be fitted.

A two-sided 0.05 significance level will be applied to each co-primary outcome, as well as each secondary outcome; no adjustment for multiple comparisons will be applied. This is consistent with the trial's objective as a pilot study to generate estimates useful for the large-scale trial to follow.

An additional advantage to using the GLMM approach is its ability to accommodate missing data (including dropouts, missed visits, and lost-to-follow-up) under a missing at random paradigm. All available follow-up data will be utilized in an intent-to-treat manner. If a participant is missing one of the follow-up time points, that participant is not completely excluded from the analysis. A supportive analysis will be conducted using multiple imputation to produce multiple datasets that have complete data for all n=60 participants, where missing values (due to dropouts, missed visits, and lost-to-follow-up) have been imputed. The statistical models will be fitted to each of the complete datasets; results of each model will be synthesized in a manner that accounts for both between and within imputation variation to produce final estimates to address the research questions.

Feasibility metrics will be computed as proportions, along with 95% confidence intervals to describe the level of uncertainty of the estimates. Lower confidence bounds of these proportions will be useful in considering worst-case scenarios when planning the subsequent large-scale trial. Acceptability data are primarily open-ended questions, and responses will be summarized to inform appropriate modifications to the PAS intervention. For the brief questionnaires on acceptability, appropriateness, and feasibility ^{95,96}, we will calculate mean and median scores and distributions across each domain.

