This will be an exploratory, single site randomized controlled trial with 60 patients equally allocated to the PAS intervention or an ATT control group (see Schema section above). Based on the ORBIT framework (which has application beyond the topic area of obesity), this study is a Phase II Preliminary Testing trial. Randomization will be stratified according to gender and presence of self-reported pain (≥3 on a 10 point scale) in any lower extremity joint (hip, knee or ankle) in addition to the surgical knee, to ensure that the groups are balanced in these respects. We chose patient-level randomization because it is a straight-forward design that avoids potential biases and challenges of cluster randomization, such as imbalances in participant characteristics across study arms and attrition of study physical therapists 41,42. With this design, each study therapist can treat patients in both study arms. Although the PAS program will involve discrete components that are distinct from usual post-TKA PT (which will be delivered to the ATT control group), we acknowledge the risk of contamination of intervention delivery. To mitigate this risk, we will employ an intensive fidelity monitoring process, described below and in the Intervention Documents. If we find in this exploratory study that contamination is a concern, clinic-level randomization will be considered for a larger trial. The typical length of post-TKA PT is about 12 weeks. We will enroll patients approximately 4 weeks from initiation of outpatient PT, allowing time for randomization and notification of the treating therapist to begin the PAS intervention before PT is complete. Follow-up assessments will be conducted 3 months after the beginning intervention visits (shortly following to the end of the PAS intervention) and after 6 months (sustainability end point). Regarding the 3-month follow-up time point, we selected this interval because it will: 1) allow for several weeks for participants to act on content delivered in the 8-week intervention visit and 2) allow sufficient time for scheduling first follow-up assessments after all intervention visits have been complete. Longer term outcomes will be included in a larger trial.

Version 11.0 6 October 2022

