6.3 MEASURES TO MINIMIZE BIAS: RANDOMIZATION AND BLINDING

The randomization scheme will be generated by the study statistician and stored within the study database. The database will be configured so that blinded study personnel (e.g., those conducting follow-up assessments) will not have access to randomization information. The participants will not be notified of randomization assignment until all baseline assessments are complete. In addition an individual participant's randomization assignment will not be known to any study personnel until baseline assessments are complete. Randomization will be stratified according to gender and presence of self-reported pain (≥3 on a 10 point scale) in any lower extremity joint (hip, knee or ankle) in addition to the surgical knee, to ensure that the groups are balanced in these respects.

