Improving Physical Activity and Gait Symmetry After Total Knee Arthroplasty Statistical Analysis Plan

NCT number NCT04090125

Document Date 10/6/2022

Statistical Design and Power

Overall Strategy, Study Design and Rationale

The Specific Aims of this study involve collection of preliminary data on the efficacy of a new Physical Activity and Symmetry (PAS) intervention, following total knee arthroplasty (TKA), and assessment of the feasibility and acceptability of the PAS intervention. To accomplish these aims, we will propose an exploratory randomized controlled trial with 60 patients equally allocated to the PAS intervention or an attention control group. Patients will be the unit of randomization. We will aim to enroll patients approximately 8 weeks 72from the initiation of outpatient PT, allowing time for randomization and notification of the treating physical therapist before PT is complete. Follow-up assessments will be conducted 8 weeks after randomization (corresponding to the end of the PAS intervention), as well as after 6 months (sustainability end point). (Longer term outcomes will be included in a larger trial.)

This study design will allow us to answer clinical questions regarding the efficacy of the PAS intervention through testing the following hypotheses:

H₁: The PAS group will have greater improvement in objectively assessed physical activity at the 8-week and 6-month assessments, compared to the attention control group. The main co-primary metric of interest is minutes of Moderate to Vigorous Physical Activity (MVPA); other secondary metrics will include step count, minutes of any physical activity, and sedentary minutes.

H₂: The post-TKA exercise group will have greater improvement in peak load symmetry during walking at the 8-week and 6-month assessments, compared to the attention control group. The main co-primary outcome of interest will be the limb symmetry index during level walking; secondary outcomes will be limb symmetry index values during additional physical performance tasks.

Analyses appropriate for randomized clinical trials, described below, will be used to test each of these hypotheses. Regarding feasibility and acceptability of the PAS intervention, simple analyses (also described below) will be used to describe metrics related to recruitment, retention, intervention delivery, and outcome assessment.

Statistical Methods

Sample Size and Power Calculations

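### Randomization is stratified by gender and other-joint pain, but the primary linear models for MVPA and load symmetry omit both factors, so the reported standard errors may be too large

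*Protocol*

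**What the plan says.** **Allocation.** Protocol 4.1: "Randomization will be stratified according to gender and presence of self-reported pain", the latter meaning a score of at least 3 out of 10 in a hip, knee or ankle other than the operated knee. Section 6.3 repeats this and gives the purpose: "to ensure that the groups are balanced in these respects". Two yes/no factors make four strata. Neither section gives a block size or says that allocation within strata is blocked. The SAP says only "Patients will be the unit of randomization" and does not mention strata.

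**Models.** For MVPA, Protocol 9.4 and the SAP both state: "Fixed effects for the primary model will include an indicator for PAS group, an indicator for the 6-month follow-up time point, their interaction". Baseline MVPA completes the list, with a random patient effect and a PAS-by-baseline term that is tested. For load symmetry (LSI), "The main difference will be to include walking speed as an additional covariate". Secondary outcomes follow the same approach. Neither stratification factor is named in any model. KOOS pain appears only in an exploratory, time-dependent analysis, and it is a different measure from pain in another joint at baseline.

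**Other ways in.** Section 9.4 says of baseline comparisons: "Variables exhibiting imbalance may be considered as covariates in the statistical models described below". The sentence defining the primary model says: "a supporting model will also include any covariates that exhibit random imbalance between groups at baseline". No threshold for imbalance is set, and the p-values are called descriptive.

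**The concern.** Stratifying on a prognostic factor removes chance differences between arms on that factor, so the treatment estimate varies less from trial to trial. A model that leaves the factor out does not know this. It still counts the factor's share of the outcome variance as noise, and so reports a standard error larger than the estimate's true variability. Confidence intervals are then too wide and the test rejects too rarely.

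The imbalance rule does not close the gap. Stratification exists to prevent the imbalance that would trigger the rule, and a triggered covariate is assured a place only in the supporting model.

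What is at stake is how uncertainty is reported in a trial expecting 54 completers, whose contrasts are meant to inform the sample size of the next trial.

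**Working it through.** **The plan's own figure.** Two-sample t-test, 27 per group, two-sided 0.05, 52 degrees of freedom, noncentrality d·√(27/2). Power is 0.438 at d = 0.5 and 0.822 at d = 0.8. The SAP table gives 0.44 and 0.82, so both reproduce, as do its other four cells. Enrolment is 54/(1 − 0.10) = 60. The table is for a comparison of means without covariates.

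**What theory predicts.** Let R² be the share of residual variance, after the baseline value, that the two factors explain. With perfect balance the true variance of the PAS contrast is proportional to 1 − R², but the model without the factors charges 1. The ratio of reported to true standard error is then about 1/√(1 − R²): 1.05, 1.12 and 1.20 at 10, 20 and 30%. Incomplete blocks and dropout loosen the balance, so the realised ratio should be lower.

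**Assumptions not in the documents.** Permuted blocks of 4 within four strata; factor prevalences 0.6 and 0.5; prognostic strength split equally between the factors; visit correlation 0.6; 6 of 60 lost at random; normal outcomes with total residual variance 1.

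**Two-visit simulation.** Random-intercept model with group, time, group by time and baseline; single-visit PAS contrast; 20,000 trials per row.

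| R² | Model SE / true SD, factors out | Ratio | Type I error, out | Model SE / true SD, factors in | Power at 0.8 SD, out / in |
|---|---|---|---|---|---|
| 0% | 0.275 / 0.276 | 1.00 | 0.053 | 0.276 / 0.277 | 0.818 / 0.817 |
| 5% | 0.275 / 0.270 | 1.02 | 0.048 | 0.268 / 0.270 | 0.822 / 0.834 |
| 10% | 0.275 / 0.264 | 1.04 | 0.043 | 0.261 / 0.263 | 0.826 / 0.854 |
| 20% | 0.275 / 0.252 | 1.09 | 0.033 | 0.246 / 0.248 | 0.838 / 0.893 |
| 30% | 0.275 / 0.239 | 1.15 | 0.025 | 0.230 / 0.232 | 0.849 / 0.929 |

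With the factors in, type I error is 0.052–0.053 throughout. The 95% interval half-width is 0.55 SD in every row without them, against 0.55/0.53/0.52/0.49/0.46 SD with them. At 0.5 SD, power out/in is 0.435/0.434, 0.435/0.472, 0.429/0.518 and 0.425/0.573 at 0/10/20/30%.

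**Checks.**
- Single-visit regression, blocks of 4 or 6, at 10/20/30%: type I error without the factors is 0.042–0.043, 0.031–0.033 and 0.025–0.027. Power at 0.8 SD is 0.83–0.84 against 0.86, 0.84 against 0.89, and 0.85 against 0.93.
- A further single-visit run with blocks of 4: model SE about 0.275 against true SD 0.264/0.249/0.240, so 4/10/15% too large. Type I error is 0.043/0.029/0.024, and power is 0.82/0.83/0.84 against 0.84/0.89/0.92.
- Varying the visit correlation (0.4 or 0.8), the prevalences (0.5 and 0.3), placing all strength in pain, or having no loss: SE 3–6% too large at 10% and 8–11% at 20%.

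**The imbalance route.** Taking chi-square p < 0.05 on all 60 as the trigger (assumed), either factor qualified in 0 of 20,000 trials with blocks of 4 and in 0 of 8,000 with blocks of 2 or of 6. Under unstratified randomization, 9–10% of trials qualified.

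**If allocation is not blocked.** With unstratified equal arms at R² = 20% (4,000 trials), model SE and true SD are both 0.271 without the factors and both 0.247 with them, and type I error is about 0.048 either way. The standard error is then correctly sized, and adjustment would sharpen the estimate itself.

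**The case against.** The strongest reply is that little is lost where it counts. This is a pilot that disclaims high power and aims to produce estimates, and the error is on the conservative side. Under blocked allocation the estimate already has the benefit of balance: at 20% its true SD falls from 0.276 to 0.252 with no covariates, and adjustment takes it only to 0.248, a further 1.6% (0.004/0.252). That stands. A reader might infer that the trial's estimate is materially less precise for want of the two terms; with blocking, it is not. The loss lies in the reported standard error, interval and test.

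It also stands that prognostic strength is assumed. Baseline MVPA or LSI may absorb much of what gender and other-joint pain would explain, and the documents give no support for 20–30% in particular. For LSI, walking speed may absorb more, and that model was not simulated.

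The reply is weaker on the imbalance rule. Section 9.4 does leave room for judgement, so a reader should not conclude that the factors could never enter. But they are assured a place only in the supporting model, and balance by design makes even that unlikely. Nor does pilot status explain analysing the data as if the strata did not exist: intervals around the contrasts are part of what the next trial will use.

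**Conclusion.** The point holds as a question of how uncertainty is reported. The primary linear models for both co-primary outcomes omit the factors used to stratify randomization. If those factors are prognostic beyond baseline and allocation is blocked, the reported standard error is too large: about 0/4/9–10/15% at an assumed 0/10/20/30% of residual variance. Type I error is about 0.05/0.043/0.03/0.025, and about 0/2–3/5/8 points of power at 0.8 SD are lost. These sizes rest on the assumed strength, blocking and normality, and they do not cover the LSI model with walking speed.

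Three stronger readings are not supported. The PAS estimate is not biased. The false-positive rate is not inflated; it is at or below nominal apart from simulation error. And power does not fall short of the plan: without the factors it is 0.82–0.85 at 0.8 SD and 0.43–0.44 at 0.5 SD, about what the SAP table states. If the factors are not prognostic, nothing is lost. The change is worth making because it is nearly free, not because the planned analysis is invalid.

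**What to change.** In Protocol 9.4 and in the SAP, add gender and other-joint pain (yes/no, as recorded for randomization) as fixed effects in the primary linear mixed models for MVPA and LSI, and in those for secondary outcomes analysed by the same linear model. State in the SAP that randomization is stratified by these two factors. The imbalance-driven supporting model can stay as it is.

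Do not carry the two terms over automatically to the logistic fallback models. There, added covariates change the meaning of a conditional odds ratio and may strain a model with about 54 patients, so that choice needs its own statement.

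The cost is a short wording change in each document and two degrees of freedom. The data are already collected for randomization. If neither factor is prognostic, simulated power at 0.8 SD is 0.817 with them and 0.818 without. If the omission is deliberate, a sentence of justification should replace the change.

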4.3 JUSTIFICATION FOR INTERVENTION

The intervention is described in detail in Section 6. The number, frequency and types of contacts were selected based on ability to deliver the PAS content, as well as feasibility of administration in real-world clinical settings. We chose for the first 2 PAS visits to be included within the context of routine post-TKA PT so that it would be integrated into routine care. The 4-week and 8-week contacts were selected to include a reasonable, feasible amount of contact – beyond the typical post-TKA time period – to follow up with patients regarding their progress with components of the PAS intervention. Because this intervention includes only 4 contacts, we have not defined a separate "minimum-acceptable" participation in the intervention. Ideal participation includes participation in all visits. As part of this exploratory trial, we will be monitoring the feasibility and rates of visit completion, in preparation for a larger trial. In this study, primary analyses will include all randomized participants, regardless of amount of intervention completion. However, we may conduct additional exploratory analyses that account for different patterns of intervention completion.

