8 STUDY ASSESSMENTS AND PROCEDURES

8.1 ENDPOINT AND OTHER NON-SAFETY ASSESSMENTS

Measures will be collected at baseline, 3 months and 6 months by a trained research assistant blinded to randomization assignment. Participants will be paid \$50 for completing baseline questionnaire and \$15 for wearing and returning an accelerometer. Then, up to \$40 at 3 month and 6 month time point: \$25 for completing questionnaires and functional measures and \$15 for wearing and returning an accelerometer. Due to COVID-19 safety measures, we may conduct a briefer set of measures focused on the primary functional assessments. We will explain to the participant during the consent process that the measures may

be more limited in order to minimize in-person visit time. Also, we may schedule a time to call the participant after the in-person visits (at baseline and 3 month and 6 month follow-up) to complete the questionnaires over the phone.

Efficacy (Aims 1 and 2)

Co-Primary Efficacy Outcome: Objectively Assessed Physical Activity (accelerometer). Our specific primary outcome of interest is MVPA per week, since this corresponds to DHHS recommendations and is a known predictor of outcomes in patients with OA ⁷. We will also examine step counts, minutes of any PA and sedentary minutes as secondary outcomes ^{72,73}. Participants will wear the waist-worn Actigraph GT3X+ (Pensacola, FL) for 7 days ⁷⁴. Following previously established thresholds, outcomes will only be computed for participants who wear the accelerometer for 4+ days with 10+ hours of wear. Accelerometers will be given to participants during in-person visits at each time point and mailed back to the study team, using our procedures from prior studies that have resulted in very high adherence rates (89-93%). If participants are not able to complete follow-up assessments in person but complete questionnaires by telephone, we may mail an accelerometer for wear and return via mail. Accelerometer data will be processed using standard procedures ⁷⁵⁻⁷⁸

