9.2 SAMPLE SIZE DETERMINATION

No adjustment for co-primary outcomes is made since this is a pilot study. We do not necessarily expect this exploratory study to be highly powered. Table 3 shows a range of effect sizes and corresponding statistical power for a comparison of intervention versus control group means, for the projected total of n=54 participants at the two-sided 0.05 significance level. We chose n=54 because this is reasonable to complete within the time frame of this exploratory trial and will allow sufficient experience to inform a larger trial. We are allowing for a 10% attrition rate, so n=60 participants will be enrolled. Data from this study are crucial for informing sample size estimates for a larger trial; however, preliminary calculations indicate that for a standardized effect size of 0.35-0.40 standard deviation units, a sample size of 100-130 per group may be required. This sample size is reasonable to enroll within the time frame of this exploratory trial, and it will allow sufficient experience with intervention delivery to inform the larger trial. Our analytic strategy (described below) will also accommodate dropout, missed visits, and loss-to-follow-up. Information regarding the actual observed extent of dropout, missed visits, and loss-to-follow-up in this study will also be useful for the subsequent large-scale trial.

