MVPA and peak joint loading symmetry during gait will be treated as co-primary outcomes. However, no adjustment for multiplicity is made due to the pilot nature of this study, with an objective of generating estimates suitable for the power analysis for the subsequent large-scale trial. Also owing to the pilot nature of this exploratory trial, we do not necessarily expect to have a highly powered study; rather, the large-scale trial that follows will aim to accomplish this objective. In the Table below we demonstrate a range of effect sizes (in standard deviation units) and the corresponding statistical power that would apply for a comparison of

intervention versus control group means at the two-sided 0.05 significance level, for the projected total of n=54 participants (n=27 per group) with complete data. Due to expected attrition of 10%, we will enroll n=60 participants into the trial. This sample size is reasonable to enroll within the time frame of this exploratory trial, and it will allow sufficient experience with intervention delivery to infer

Statistical power according to effect size,					
assuming 27 patients per group					
Effect Size (SD units)					
0.5	0.6	0.7	0.8	0.9	1.0
0 44	0.58	0.71	0.82	0.90	0.95

and it will allow sufficient experience with intervention delivery to inform the larger trial. Our analytic strategy (described below) will also accommodate dropout, missed visits, and loss-to-follow-up. Information regarding the actual observed extent of dropout, missed visits, and loss-to-follow-up in this study will also be useful for the subsequent large-scale trial.

Analytic Techniques and Handling of Missing Data

Preliminary analyses will include generating descriptive statistics for demographic variables, as well as baseline characteristics and follow-up measures. This includes means and standard deviations for continuous variables, and frequencies and percentages for categorical variables. Ranges will also be examined for outliers and to ensure data integrity. Demographics and baseline characteristics will also be described separately by randomized group. Statistical tests will be performed to compare each of these by randomized group to determine the extent of random imbalance by t-test of chi-square testing, as appropriate. However, the p-values generated by these tests are considered as descriptive rather than as inferential. We would

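### The primary MVPA model drops any randomized participant whose baseline accelerometer wear was insufficient, even with valid follow-up, and no primary-analysis rule prevents this

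*Protocol*

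**What the plan says.** Protocol section 9.4 and the SAP (Analytic Techniques and Handling of Missing Data) specify the MVPA model in the same words. The response vector holds the two follow-up values only. The fixed effects are group, "an indicator for the 6-month follow-up time point, their interaction (group by time), and baseline MVPA value".

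Protocol section 8.1 decides when an MVPA value exists: "outcomes will only be computed for participants who wear the accelerometer for 4+ days with 10+ hours of wear".

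On the analysis population, section 9.3 calls the primary analyses intent-to-treat. Section 4.3 says that "primary analyses will include all randomized participants, regardless of amount of intervention completion". Section 9.4 says: "All available follow-up data will be utilized in an intent-to-treat manner". The missing-data text in section 9.4 then assures the reader that missing one follow-up does not remove a participant. It says nothing about a missing baseline. Multiple imputation for all 60 is labelled supportive, and the causes of missingness it lists are dropout, missed visits and loss to follow-up. Insufficient wear is not listed.

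On timing, section 5.5 has the assignment call follow receipt of the device. Section 6.3 withholds assignment until baseline assessments are complete. Neither section says that complete means valid wear, and neither provides for a repeat wear period. Under section 7.2, nobody is replaced once told their assignment.

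**The concern.** A likelihood-based mixed model uses whatever responses a participant has, which is the advantage section 9.4 claims for it. That advantage does not extend to covariates: if baseline MVPA is missing, every follow-up row for that participant leaves the fit. A participant who returns the accelerometer with too few valid days can still be randomized, attend both follow-ups and supply two valid MVPA values, yet contribute nothing to the co-primary analysis.

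The model as written would then not deliver the population the plan promises. In a trial of 60, each lost participant costs precision. The contrasts at stake are those that section 9.4 says will feed the sample size of the next trial. Without a stated rule, either software deletes these participants by default or someone chooses a remedy after seeing the data.

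**Working it through.** **Inputs**
- Projected completers: "for the projected total of n=54 participants at the two-sided 0.05 significance level" (Protocol 9.2), with the SAP power table "assuming 27 patients per group".
- Randomized: "60 patients equally allocated to the PAS intervention or an attention control group" (SAP), allowing 10% attrition.
- Accelerometer adherence in the team's prior studies: 89-93% (Protocol 8.1). This is not stated to be valid wear or specific to baseline.

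**Step 1: reproduce the plan's figures.** Enrolment is 54 / 0.90 = 60, as stated. Power is taken from a two-sample t-test with n per arm, 2n − 2 degrees of freedom and noncentrality d × √(n/2). For n = 27 there are 52 degrees of freedom, and at d = 0.8 the noncentrality is 0.8 × √13.5 = 2.94.

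| Effect (SD) | 0.5 | 0.6 | 0.7 | 0.8 | 0.9 | 1.0 |
|---|---|---|---|---|---|---|
| SAP | 0.44 | 0.58 | 0.71 | 0.82 | 0.90 | 0.95 |
| Recomputed | 0.438 | 0.581 | 0.714 | 0.822 | 0.901 | 0.950 |

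The SAP row reproduces. The Protocol's copy of the table differs at 0.6 and 0.7 SD, possibly through text extraction. Both documents give 0.82 at 0.8 SD, the value used below.

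**Step 2: confirm the mechanism.** A model of the stated form was fitted to simulated data: 54 participants, two follow-ups each (108 rows), all responses present, five baselines missing. The fit kept 108 − 5 × 2 = 98 rows and 54 − 5 = 49 participants.

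**Step 3: size the loss.** Let r be the proportion of randomized participants with a valid baseline, assumed independent of attrition. The number of randomized participants affected is 60 × (1 − r), and the number of completers fitted is 54 × r.

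| r | Affected of 60 | Fitted of 54 | Per arm | Power at 0.8 SD |
|---|---|---|---|---|
| 0.89 | 6.6 | 48.1 | about 24 | 0.77 |
| 0.93 | 4.2 | 50.2 | about 25 | 0.79 |
| 0.98 | 1.2 | 52.9 | about 26.5 | 0.81 |
| 1.00 | 0 | 54 | 27 | 0.82 |

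The rows for 0.89 and 0.93 treat the whole adherence shortfall as invalid baseline wear. The row for 0.98 is an assumed milder case. The t-test ignores the precision gained from baseline adjustment and repeated measures, so these powers are indicative only.

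**The case against.** The strongest reply is that few such participants will exist. Sections 5.5 and 6.3 together should keep people who never return the device out of the 60, so only those who return it with too little wear are at risk. The 89-93% figure describes adherence to the hand-out and mail-back procedure in other studies. This stands: 4-7 of 60 is an assumption and an upper range. It does not close the gap, because valid wear is nowhere made a condition of assignment.

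Second, the sentence in section 4.3 about all randomized participants goes on to speak of intervention completion, so it mainly concerns adherence to the intervention. That is fair. The conflict rests more firmly on the section 9.4 sentence about available follow-up data and the intent-to-treat statement in section 9.3. It is also fair that the plan nowhere states that these participants are deleted. Deletion follows from fitting the model as specified.

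Third, the supportive imputation aims at complete data for all 60 and could recover these participants. It could, but not in the primary analysis, and insufficient wear is not among its listed causes.

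Two stronger readings are tempting and not supported:
- **A much smaller analysed sample.** A reader might apply the wear rate at baseline and again at follow-up: 54 × 0.89² = 42.8 to 54 × 0.93² = 46.7. That counts one invalid follow-up as loss of the participant, but there are two follow-ups and section 9.4 keeps anyone missing only one. With independent wear failures, a valid baseline plus at least one valid follow-up gives 54 × 0.89 × (1 − 0.11²) = 47.5 to 54 × 0.93 × (1 − 0.07²) = 50.0. Follow-up wear is in any case a separate matter.
- **Bias between arms.** The baseline wear period ends before assignment is disclosed, so exclusion for invalid baseline wear cannot be driven by knowledge of the arm. The comparison among those retained is still randomized.

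**Conclusion.** The point holds at a modest size. As specified, the primary MVPA model leaves out any randomized participant with insufficient baseline wear, and the primary analysis has no rule to prevent it. That departs from the plan's own commitment on follow-up data and intention to treat.

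The documents do not give the number affected. Over the assumed range it runs from about 1 to about 7 of 60, with power at 0.8 SD between about 0.81 and 0.77 against the stated 0.82. The upper end requires the whole prior-study shortfall to be invalid baseline wear among people who were nonetheless randomized. If poor wearers at baseline are also poor wearers later, part of this loss would occur anyway.

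The consequence is lost precision and an analysis population narrower than stated. The Protocol does not expect this pilot to be highly powered (section 9.2), so the power change is not decisive in itself. The case for acting is that the stated model falls short of the stated principle and the remedy is nearly free.

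**What to change.** State in section 9.4 and the SAP how a missing baseline is handled in the primary model. Either option serves:
- Keep baseline MVPA as a covariate, fill a missing value with the overall baseline mean computed without regard to arm, and add a missing-baseline indicator. This changes the planned model least.
- Model baseline and both follow-ups jointly as responses, with a common baseline mean for the two arms (a constrained longitudinal model). The planned PAS-by-baseline term cannot then be entered as written, so move it to a separate exploratory model among participants with an observed baseline.

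Apply the same rule to any other outcome whose baseline is missing. The limb symmetry index has no wear rule and is measured at the in-person visit, so it may seldom be needed there. It may matter for balance, since section 10.4 records that those tests were paused and later resumed in reduced form.

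Also state that the supportive multiple imputation covers values missing through insufficient wear, at baseline as well as at follow-up.

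The cost is a few sentences of SAP text and a few lines of model code. No new data or participants are needed.
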